8.2 Secondary Efficacy Analysis

8.2.1 Secondary Efficacy Endpoints

The key secondary efficacy endpoints include the following:

- Duration of severe thrombocytopenia defined as a platelet count $< 50 \times 10^9/L$ during the period after post-chemotherapy IP treatment in Cycle X+1 through Chemotherapy Day of Cycle X+2

Confidential

Duration of severe thrombocytopenia will be assessed as the total number of days with platelet count $<50 \times 10^9/L$ based on platelet counts taken from the day after the last post-chemotherapy IP in Cycle X + 1 through the Chemotherapy Day in Cycle X + 2. Platelet counts collected through the expected date of Cycle X+2 Chemotherapy Day (based on 21- or 28-day cycle length after Cycle X+1 Chemotherapy Day) or the end of study date, whichever is earliest, will be considered for this endpoint.

The days between a platelet count $<50 \times 10^9/L$ and a subsequent platelet count assessment will be assumed to show severe thrombocytopenia and contribute to the duration, and days between a platelet count $\geq 50 \times 10^9/L$ and a subsequent platelet count within Cycle X+1 will not contribute to the duration. If a scheduled platelet count assessment is missing, it will be considered that the platelet count was $<50 \times 10^9/L$ at that visit.

- Change in platelet count from baseline (qualifying chemotherapy cycle [Cycle X]) (nadir) to Cycle X + 1 (nadir)

Change in platelet count from baseline is the difference between the lowest platelet value prior to the first dose of study treatment and the lowest value during Cycle X+1 (i.e., the lowest platelet value during the day after the last post-chemotherapy IP dose in Cycle X + 1 through the Chemotherapy Day of Cycle X + 2).

Multiple imputation methods using a "jump to control" procedure will be implemented to address missing Cycle X+1 (nadir). In this procedure, multiply imputed datasets will be produced using SAS PROC MI which assume that the subjects with missing Cycle X+1 (nadir) have platelet counts following a similar pattern of those subjects receiving placebo. The multiply imputed datasets are then combined using SAS PROC MIANALYZE to create a p-value for the assessment of the difference between avatrombopag and placebo groups in the mean change in platelet count from baseline. This p-value will be used in the hierarchical testing strategy defined in Section 8.2.2.

- Proportion of subjects who do not have major or non-major clinically relevant bleeding during the period after post-chemotherapy IP treatment in Cycle X+1 through Chemotherapy Day of Cycle X + 2

Subjects will be considered to NOT have major or non-major clinically relevant bleeding if no bleeding events were reported on the ISTH Non-surgical Bleeding Assessment CRF page that were classified as "Major Bleeding" or "Non-major clinically relevant bleeding" from the day after the last post-chemotherapy IP in Cycle X + 1 through the Chemotherapy Day in Cycle X+2. If information on the bleeding events is missing, subjects will be assumed to have had major or non-major clinically relevant bleeding during that period.

- Proportion of subjects who do not receive platelet transfusion during the period after post-chemotherapy IP treatment in Cycle X+1 through Chemotherapy Day of Cycle X + 2

Subjects will be considered to have not required a platelet transfusion if subjects did not require a platelet transfusion after taking the last post-chemotherapy IP in Cycle X + 1 through the Chemotherapy Day in Cycle X + 2. If information on platelet transfusion is missing, subjects will be assumed to have had a platelet transfusion during that period.

The categorical variables (eg, proportion) will be summarized and analyzed in the same manner as the primary efficacy endpoint. If the data is sparse where the

Confidential

approximative methods cannot be applied, the Fisher's Exact test will be used instead.

For continuous variables (eg, change from baseline in platelet count, duration of severe thrombocytopenia), the normality assumption of an analysis of covariance will be evaluated analytically using the Shapiro-Wilk test and visually using the residual plot.

Plots will be created displaying platelet count values over time separately for the Double-Blind/Observational period, the OLE period, and the entire study.

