## 4 SELECTION AND WITHDRAWAL OF SUBJECTS

### 4.1 Inclusion Criteria for All Subjects

Subjects who meet all of the following criteria will be eligible to participate in the study:

1. Subject is  $\geq 18$  years of age at the time of informed consent;
2. Subject with a diagnosis with ovarian cancer, lung cancer (small cell or non-small cell), or bladder cancer, requiring systemic chemotherapy;
3. Subject is currently receiving a chemotherapy regimen given in a 21-day or 28-day cycle (other chemotherapy cycle lengths are not allowed), including 1 or more of the following agents or class of agents:
  - o Nucleoside analog, including gemcitabine and fluorouracil;
  - o Carboplatin or cisplatin;
  - o Anthracycline; or
  - o Alkylating agent;
4. Subject experienced severe thrombocytopenia, defined as 2 platelet counts  $< 50 \times 10^9/L$  measured at least 24 hours apart, during the qualifying chemotherapy cycle (Cycle X), of their current chemotherapy regimen. Platelet counts obtained per standard of care during Cycle X prior to consent may be used;
5. Subject is planned to receive the same chemotherapy regimen and the same dose(s) on Chemotherapy Day (Days 1-3) of Cycle X+1 as was given in the qualifying chemotherapy Cycle X;
6. Subject has an Eastern Cooperative Oncology Group (ECOG) performance status  $\leq 2$ ;
7. Subject has a life expectancy  $> 12$  weeks at Screening and is able to receive at least 2 additional cycles of the current chemotherapy regimen;
8. Females of childbearing potential must agree to use a highly effective method of contraception (eg, total abstinence; an intrauterine device; hormonal contraceptive given orally, by injection, or by implant; double barrier contraception (i.e., condom + diaphragm); or has a vasectomized partner with confirmed azoospermia) throughout the entire study period and for 30 days after investigational product (IP) discontinuation. If currently abstinent, the subject must agree to use an effective method as described above if she becomes sexually active during the study period or for 30 days after IP discontinuation.

Male subjects must be either surgically sterile or agree to use a double barrier contraception method (combination of male condom with either cap, diaphragm, or sponge with a spermicide) throughout the entire study period and for 30 days after IP discontinuation;

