### **6.3.3 Cycle X + 1 Days 11 ( $\pm 1$ day), 15 ( $\pm 1$ day), and 18 ( $\pm 1$ day) (Visits 6, 7, and 8)**

The following procedures will be performed on Cycle X + 1, Days 11, 15, and 18 at Visits 6, 7, and 8:

- Record concomitant medications;
- Assess adverse events;
- Collect blood samples for platelet counts;
- Assess chemotherapy dose modifications/schedule; and
- Assess whether subject required platelet transfusion.

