4.1.2 Visit Windows

No formal visit windowing will be conducted. For by-visit/by-cycle tabular summaries, the scheduled visits or actual chemotherapy cycles will be used in the analyses. The exception to this is for nadir platelet counts; both scheduled and unscheduled platelet counts will be considered for designation of the nadir value within a cycle.

For analyses considering the worst post-baseline grade (laboratory shift tables) or post-baseline liver tests, all post-baseline values will be considered.

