4.3.2 Platelet Counts

Platelet counts are collected at local laboratories for eligibility and efficacy assessments. Platelet count is also included in the hematology panel sent to the central laboratory as a safety evaluation. For the efficacy analyses, only platelet counts assessed by the local laboratories will be included in the calculations and summaries. For the safety analyses, only platelet counts assessed by the central laboratory will be included in the summaries.

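### In the Step 1 duration endpoint a missed scheduled platelet count is scored below 50 even when a nearby unscheduled local count shows 50 or more, and the SAP does not say whether unscheduled counts enter that endpoint

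*SAP*

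**What the plan says.** SAP 8.2.1 totals, for each subject, the days with a platelet count below 50 × 10⁹/L (all counts below are in these units), "based on platelet counts taken from the day after the last post-chemotherapy IP" in Cycle X+1 up to Chemotherapy Day of Cycle X+2, and no later than the date on which that day was due. Two rules turn counts into days:

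- **Interval rule.** The days between a count below 50 "and a subsequent platelet count assessment will be assumed to show severe thrombocytopenia and contribute to the duration". A count of 50 or more adds no days up to the next count.
- **Missing-visit rule.** "If a scheduled platelet count assessment is missing, it will be considered that the platelet count was" below 50 at that visit. No condition is attached.

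SAP 4.1.2 states "No formal visit windowing will be conducted" and makes one exception: "both scheduled and unscheduled platelet counts will be considered for designation of the nadir value within a cycle". SAP 4.3.2 adds that for efficacy "only platelet counts assessed by the local laboratories will be included in the calculations and summaries". No sentence says whether unscheduled local counts enter the duration, or what happens when one lies beside a missed visit.

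The schedule is sparse. Protocol 6.3.3 reads "The following procedures will be performed on Cycle X + 1, Days 11, 15, and 18 at Visits 6, 7, and 8", each with a tolerance of ±1 day; the next scheduled count is on Chemotherapy Day of Cycle X+2. Protocol 4.1 admits both cycle lengths: "Subject is currently receiving a chemotherapy regimen given in a 21-day or 28-day cycle". Under SAP 8.2.2, failure on duration (Step 1) stops Steps 2 to 4.

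**The concern.** The missing-visit rule is triggered by the absence of a scheduled assessment, not by the absence of data. A programmer who follows it would place a value below 50 on the target day even when the subject's own local counts on either side are 50 or more, and would count severe days from it until the next count. The same subject could have a Step 2 nadir of 50 or more, because the nadir accepts unscheduled counts, and a positive Step 1 duration over the same period.

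At stake is the first gate of the key secondary family. False severe days add noise to the endpoint, and they add bias if the arms miss visits at different rates. The nadir, bleeding and transfusion tests all depend on passing Step 1.

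Nearby local counts are plausible. Protocol 4.1 accepts standard-of-care counts for eligibility, and SAP 9.4.6 describes an eCRF page that records visits not done because of COVID-19. Neither gives a frequency.

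**Working it through.** **The plan's own figure.** The only power calculation is for the primary endpoint (SAP 3.3: 40% v 10%, 2:1, 90% power, two-sided 0.05, 10% premature termination, 120 subjects). The pooled normal formula gives a placebo arm of n = [1.960·√(0.30·0.70·1.5) + 1.282·√(0.10·0.90 + 0.40·0.60/2)]² / 0.30² = 31.6. The continuity correction, (n/4)·[1 + √(1 + 3/(0.30n))]², raises it to 36.46. The total is 3 × 36.46 = 109.4, and 109.4/0.9 = 121.5 (or 109.4 × 1.1 = 120.3), close to 120. This figure is unaffected. No power, effect size or missed-visit rate is stated for Step 1.

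**Worked cases.** False days = day of the next count minus target day of the missed visit. All measured counts are 50 or more. With Chemotherapy Day on Day 1, the last usable day is 1 + 21 = 22 or 1 + 28 = 29.

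| Missed visit | Measured counts nearby | Unscheduled counts enter | Unscheduled counts left out | With the fix |
|---|---|---|---|---|
| Day 15 | Day 13 unscheduled, Day 18 | 18 − 15 = 3 | 3 | 0 |
| Day 18, 28-day cycle | Day 16 unscheduled, Day 29 | 29 − 18 = 11 | 11 | 0 |
| Day 18, 21-day cycle | Day 16 unscheduled, Day 22 | 22 − 18 = 4 | 4 | 0 |
| Day 18, 28-day cycle | Day 20 unscheduled, Day 29 | 20 − 18 = 2 | 29 − 18 = 11 | 0 |

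When the unscheduled count comes before the missed visit, both readings charge the same days. When it comes after, the answer depends on the point that the SAP leaves open (2 v 11 in the last row).

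The visit tolerance limits which cases qualify. Visit 7 may fall on Days 14 to 16 and Visit 8 on Days 17 to 19, so a count on Day 14 or 16 (for Visit 7) or Day 17 (for Visit 8) may already be the visit. Day 13 lies outside both the Visit 6 window (Days 10 to 12) and the Visit 7 window. The Day 16 rows assume that Visit 7 was done separately, on Day 14 or 15. If the Day 16 draw is itself Visit 7, the fix below does not reuse it and the days remain.

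**Simulation, equal missingness.** There were 80 v 40 subjects, 1,000 runs, a two-sided 0.05 Wilcoxon test, and rejections counted only in favour of avatrombopag. Assumed, because the documents are silent: nadir near Day 14, 30% of subjects on 28-day cycles, the missed-visit rates shown, and an unscheduled count 1 to 2 days from 50% or 100% of missed visits. The fix simulated is the basic one (a count within 2 days replaces the missed visit), without the reuse and tie rules.

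| Missed | Nearby count | Complete data | As written, unscheduled enter | As written, unscheduled left out | Fix |
|---|---|---|---|---|---|
| 5% | 50% | 93% | 87% | 85% | 89% |
| 5% | 100% | 94% | 89% | 87% | 94% |
| 10% | 50% | 93% | 79% | 77% | 85% |
| 10% | 100% | 93% | 82% | 76% | 93% |
| 20% | 50% | 93% | 65% | 59% | 75% |
| 20% | 100% | 92% | 69% | 57% | 91% |

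Fix minus as written (unscheduled counts entering) is 2 to 5 points at 5% missed, 6 to 11 at 10% and 10 to 22 at 20%.

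**Simulation, unequal missingness.** This uses a second setting with complete-data power of about 73%, a nearby count for 50% of missed visits, and unscheduled counts entering.

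| Truth | Missed, avatrombopag v placebo | As written | Fix |
|---|---|---|---|
| Effect | 5% v 15% | 92% | 86% |
| Effect | 15% v 5% | 14% | 34% |
| No effect | 5% v 15% | 17% | 8% |
| No effect | 10% v 10% | 2.9% | 3.3% |

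The nominal rate in this direction is 2.5%. Simulation error is about 1 to 1.5 points for most entries; for example √(0.79·0.21/1000) = 1.3 points.

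**The case against.** A reader might infer three stronger things, none of which the documents support.

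- **That measured recovery is overwritten.** No sentence discards an unscheduled count. SAP 8.2.1 speaks of counts taken in the window and does not limit them to scheduled ones. If they enter, a count of 50 or more shortly after the missed visit ends the imputed run. The measured data are contradicted rather than deleted.
- **That SAP 4.1.2 bars unscheduled counts from the duration.** The sentences after the no-windowing statement concern tabular summaries by visit or cycle, and duration is a per-subject total. The SAP is silent on the point.
- **That the rule simply costs power.** It does so with equal missingness or with more missed visits on avatrombopag. With more on placebo it raises the rejection rate, including when there is no effect.

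Other objections stand in part. Worst-case imputation is the SAP's consistent choice (4.3.5, 8.1 and the bleeding and transfusion endpoints in 8.2.1) and is defensible where nothing was measured; the issue is its use where something was. Steps 1 and 2 may handle missing data differently without contradiction. Much of the simulated loss comes from visits with no nearby count: at 10% missed and 50% nearby, power falls 14 points (93% to 79%) and the fix recovers 6. The simulation also counts draws 1 day from the target, which sites may already log as the visit, so it may overstate the gap. The 11 days owe much to the lack of any scheduled count between Day 18 and the next cycle.

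The unconditional rule itself remains unanswered.

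**Conclusion.** The concern holds as a defect in a stated rule with an unstated companion: the rule imputes severe thrombocytopenia without looking at nearby measured counts, and the status of unscheduled counts in the gating endpoint is undefined. Per affected subject the error is 3 days (Day 15 missed, 50 or more on Days 13 and 18) and up to 11 days (Day 18 missed in a 28-day cycle, 50 or more on Days 16 and 29, with Visit 7 done separately). These follow from the SAP's text alone.

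The effect on the Step 1 test cannot be derived from the documents. The power and false-rejection figures rest on assumed platelet curves, missed-visit rates and availability of nearby counts, and show direction rather than expected size. Under equal missingness the type I error stays near nominal. Under unequal missingness the rule can err either way; using the nearby count reduces the error but does not remove it (17% to 8% against 2.5%). The primary endpoint and its sample size are untouched. The rule is worth correcting before database lock and unblinding.

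**What to change.** Amend the duration text in SAP 8.2.1 to state:

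1. All local platelet counts in the window, scheduled or unscheduled, enter the duration on their actual dates.
2. A missed scheduled assessment is taken as below 50 only if no unscheduled local count exists within 2 days of its target day.
3. An unscheduled count may stand in for one missed visit only: the nearest or, if two are equally near, the earlier.
4. A count already serving as another scheduled visit may not be reused.
5. If two counts are equally near a missed visit, the lower decides its status.

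It helps to add that a stand-in of 50 or more only blocks the imputed value and does not shorten a run of severe days begun by an earlier measured low count. Rules 3 to 5 are needed because a 2-day window overlaps between visits: Day 13 is within 2 days of both Day 11 and Day 15.

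Keep the present rule as a sensitivity analysis and report missed scheduled counts by arm, since the direction of any bias depends on the difference.

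Cost: a few lines of SAP text and minor programming, with no new data. Protocol 10.2.1.2 contains no imputation rule for duration, so the change stays within the SAP. The imputation becomes slightly less conservative where a nearby count exists and is unchanged where none does.

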**Analysis of Other Efficacy Endpoints:**

The categorical variables (eg, proportion) will be summarized and analyzed in the same manner as the primary efficacy endpoint. The continuous variables (eg, change from baseline in platelet count) will be analyzed using analysis of covariance models with treatment and the randomization stratification factor as main effects and the baseline measurement as a covariate, and Wilcoxon Rank Sum tests if the normality assumption is violated.

The efficacy variables collected during the optional OLE Period will be summarized descriptively.

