### 5.3 Randomization and Blinding

This is a randomized, double-blind, placebo-controlled study. For the Double-Blind Treatment Period, subjects who meet the inclusion criteria and exclusion criteria will be randomized to receive either avatrombopag 60 mg or placebo in a 2:1 ratio at the Baseline Visit. Randomization will be stratified by the number of chemotherapy agents the subject is receiving (1, ≥2 permissible chemotherapy agents [nucleoside analog, including gemcitabine and fluorouracil; carboplatin or cisplatin; anthracycline; or alkylating agent]). Randomization assignment will be performed using interactive response technology (IRT). Following randomization, IP will be dispensed in a double-blind manner. The Sponsor and designated clinical site personnel (Investigator and study coordinator) will be blinded to the treatment group for each subject. Subjects will also be blinded to the treatment they receive.

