### 10.2.1.3 Other efficacy analysis

The other efficacy endpoints include the following during the period after post-chemotherapy IP treatment in Cycle X+1 through Chemotherapy Day of Cycle X+2:

- Proportion of subjects who do not have a chemotherapy dose reduction that is  $\geq 15\%$  due to thrombocytopenia;
- Proportion of subjects who do not have a chemotherapy delay that is  $\geq 4$  days due to thrombocytopenia;
- Proportion of subjects with a pre-defined post-baseline nadir platelet count; and
- Proportion of subjects achieving a pre-defined post-baseline maximum platelet count.

The categorical variables (eg, proportion) will be summarized and analyzed in the same manner as the primary efficacy endpoint. The continuous variables (eg, change from baseline in platelet count) will be analyzed using analysis of covariance models with treatment and the randomization stratification factor as main effects and the baseline measurement as a covariate, and Wilcoxon Rank Sum tests if the normality assumption is violated.

The efficacy variables collected during the optional OLE Period will be summarized descriptively.

Additional efficacy analyses will be performed if deemed necessary. The details of the analyses will be described in the Statistical Analysis Plan that will be finalized prior to database lock.

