4.3.4 Definition of Baseline

For data displays for the Double-Blind/Observational Period, a baseline value will be the last non-missing value taken prior to the start of study treatment in the Double-Blind Period, unless otherwise indicated. For the efficacy analyses of platelet count, baseline will be defined as the lowest platelet count collected during the qualifying period in Cycle X and prior to the first dose of study drug.

For data displays for the OLE Period, a baseline value is the last non-missing value taken prior to the start of the pre-chemotherapy IP of Cycle X+3, unless otherwise indicated. For the efficacy analyses of platelet count, baseline will be defined as the lowest platelet count collected during Cycle X+2 and prior to the pre-chemotherapy IP of Cycle X+3.

Confidential

For data displays for the entire study (avatrombopag group only), a baseline value will be the last non-missing value taken prior to the start of study treatment in the Double-Blind Period, unless otherwise indicated. For the efficacy analyses of platelet count, baseline will be defined as the lowest platelet count collected during the qualifying period in Cycle X and prior to the first dose of study drug.

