8.1 Primary Efficacy Analysis

The primary efficacy endpoint is the proportion of responders who meet all of the following criteria during the period after post-chemotherapy IP treatment in Cycle X+1 through Chemotherapy Day of Cycle X+2:

- Not requiring a platelet transfusion;
- Not requiring a chemotherapy dose reduction by $\geq 15\%$ due to thrombocytopenia; and
- Not requiring a chemotherapy delay by ≥ 4 days due to thrombocytopenia.

Chemotherapy Day is defined as the latest among Day 1 to 3 of the subject's chemotherapy regimen (eg, if chemotherapy is given on Day 1 and Day 2, Day 2 will be the Chemotherapy Day). For subjects whose chemotherapy is on an intermittent schedule (eg, Days 1, 8, 15), Day 1 will be the Chemotherapy Day.

If subjects had no post-chemotherapy IP dosing in Cycle X+1, the assessment period of the primary efficacy endpoint will start from the day after Chemotherapy Day in Cycle X+1 through Chemotherapy Day in Cycle X+2.

If subjects had any post-chemotherapy IP dosing in Cycle X+1, the assessment period of the primary efficacy endpoint will start from the day after post-chemotherapy IP dosing in Cycle X+1 through Chemotherapy Day in Cycle X+2.

If the information on platelet transfusion or chemotherapy dose reduction or delay is missing (eg, due to early drop-out), the subject will be treated as a non-responder in the primary analysis.

The primary efficacy endpoint will be tested between avatrombopag and placebo using the Cochran-Mantel-Haenszel (CMH) 2-sided test at $\alpha=0.05$, adjusting for number of eligible chemotherapy agents as collected in the IWRS (1 or ≥ 2 permissible chemotherapy agents). The numbers and percentages of responders in each treatment group with the associated unadjusted exact (Clopper-Pearson) 95% CI, and the difference in proportion of responders between avatrombopag and placebo with the associated unadjusted exact (Clopper-Pearson) 95% CI will be calculated. The primary analysis will be performed based on the FAS and repeated on the PPS as a supportive analysis.

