8.2.2 Hierarchical Testing Strategy for Secondary Efficacy Endpoints

If the test of the treatment effect on the primary efficacy endpoint is statistically significant, the analysis of the key secondary efficacy endpoints will proceed using the following step-down closed testing procedure to maintain the family-wise Type I error rate at significance level $\alpha = 0.05$ (2-sided):

- Step 1: Test the treatment effect at a significance level of 0.05 on duration of severe thrombocytopenia defined as a platelet count $<50 \times 10^9/L$ during the period after post-chemotherapy IP treatment in Cycle X+1 through Chemotherapy Day of Cycle X + 2; if successful, proceed to Step 2; otherwise stop at Step 1.
- Step 2: Test the treatment effect at a significance level of 0.05 on change in platelet count from baseline (qualifying chemotherapy cycle [Cycle X]) (nadir) to Cycle X + 1 (nadir); if successful, proceed to Step 3; otherwise stop at Step 2.
- Step 3: Test the treatment effect at a significance level of 0.05 on proportion of subjects who do not have major or non-major clinically relevant bleeding during the period after post-chemotherapy IP treatment in Cycle X+1 through Chemotherapy Day of Cycle X + 2; if successful, proceed to Step 4; otherwise stop at Step 3.
- Step 4: Test the treatment effect at a significance level of 0.05 on proportion of subjects who do not receive platelet transfusion during the period after post-chemotherapy IP treatment in Cycle X+1 through Chemotherapy Day of Cycle X + 2.

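### The only fallback test documented for Step 1 (duration of severe thrombocytopenia) states no stratification; naming a stratified Wilcoxon test in the SAP is a cheap improvement

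*SAP*

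**What the plan says.** SAP 8.2.2 opens the key secondary hierarchy with Step 1: "Test the treatment effect at a significance level of 0.05 on duration of severe thrombocytopenia". It names no test. If Step 1 fails, nadir change, bleeding and platelet transfusion are not formally tested.

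SAP 8.2.1 defines the outcome as a day count ("Duration of severe thrombocytopenia will be assessed as the total number of days with platelet count" below 50 × 10⁹/L) and counts the whole interval from a low count to the next count. For continuous variables, with duration given as an example, it says that "the normality assumption of an analysis of covariance will be evaluated analytically using the Shapiro-Wilk test and visually using the residual plot". It gives no Shapiro-Wilk cut-off, no rule for when test and plot disagree, no model terms and no alternative test.

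The alternative appears only in the protocol, in 10.2.1.3 and the matching synopsis text. The first branch there is "analysis of covariance models with treatment and the randomization stratification factor as main effects and the baseline measurement as a covariate". The second branch carries no mention of the stratum; it reads in full: "and Wilcoxon Rank Sum tests if the normality assumption is violated". Both stand under other efficacy endpoints. All four of those are proportions, so in practice the text can only serve the continuous key secondary endpoints. Protocol 10.2.1.2 names no test for them.

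The stratum is used elsewhere. Protocol 5.3: "Randomization will be stratified by the number of chemotherapy agents the subject is receiving". SAP 8.1 runs the primary CMH test "adjusting for number of eligible chemotherapy agents as collected in the IWRS".

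**The concern.** Read together, the documents give Step 1 a two-branch rule: an ANCOVA that adjusts for the stratum, or a Wilcoxon rank sum test for which no stratification is stated. If the number of agents predicts thrombocytopenia, the unstratified rank test leaves between-stratum variation in the comparison. It then becomes conservative and loses power at the gate to the other three key secondary endpoints, one of which, bleeding, answers a stated secondary objective.

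The choice of branch also rests partly on reading a residual plot, with no stated criterion for which p-value decides Step 1.

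**Working it through.** **The plan's own figure.** The documents state no power for Step 1, only N = 120 for the primary endpoint. Inputs (Protocol 10.2.4): 10% vs 40%, ratio k = 2, two-sided alpha 0.05, power 90%, 10% dropout. Pooled rate = (0.10 + 2 × 0.40)/3 = 0.30.
- Placebo n = [1.96·√(0.30·0.70·1.5) + 1.2816·√(0.10·0.90 + 0.40·0.60/2)]² / 0.30² = 31.6. Total 94.9; divided by 0.9, 105.4.
- With continuity correction: (31.63/4)·[1 + √(1 + 3/(31.63·0.30))]² = 36.5. Total 109.4; divided by 0.9, 121.5, close to 120.

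N = 120 (80/40) is therefore used below.

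**Values that duration can take.** Assume nominal days, chemotherapy on Day 1 and no unscheduled counts. Protocol 6.3.3 schedules counts on Days 11, 15 and 18; the next is Day 22 (21-day cycle) or Day 29 (28-day cycle).
- 21-day cycle: intervals of 4, 3 and 4 days. Subset sums are 0, 3, 4, 7, 8, 11: 6 values.
- 28-day cycle: intervals of 4, 3 and 11 days. Subset sums are 0, 3, 4, 7, 11, 14, 15, 18: 8 values.
- If a low final count earns one day, which the SAP does not settle, these become 10 and 14 values.

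**Simulation inputs (all assumed; the documents give none).** 128 scenarios × 1,500 trials; permuted blocks of 3 within stratum; latent-normal platelet level at Days 11, 15, 18 and the final day; subject SD 1, visit SD 0.6; treatment shift 0 or 0.6; stratum shift 0, 0.5, 1 or 2; two baseline levels; 50% or 80% of subjects with ≥2 agents; 0% or 30% on 28-day cycles; final-day convention 0 or 1 day; visit jitter ±1 day; Cycle X nadir correlated 0.4 with the subject level. The two-branch rule is taken as: Shapiro-Wilk p < 0.05 on residuals of the ANCOVA with nadir leads to plain Wilcoxon, otherwise that ANCOVA decides. Monte Carlo SE is about 0.6 points for type I error and 1.2 for power.

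| Stratum effect (placebo subjects with any severe day, 1 vs ≥2 agents) | Van Elteren minus plain Wilcoxon, power points | Van Elteren minus two-branch rule | Shapiro-Wilk rejects (nadir in model) |
|---|---|---|---|
| None | -0.7 to +0.3 | -0.7 to +0.3 | 94-100% |
| Small (65% vs 80%, or 37% vs 55%) | 0.2 to 1.5 | -0.1 to +1.5 | 88-100% |
| Moderate (56% vs 86%, or 29% vs 63%) | 2 to 6 | -0.7 to +5.3 | 61-100% |
| Strong (38% vs 94%, or 15% vs 79%) | 9-14 (20/80 split), 18-26 (50/50) | 2 to 20 | 39-98% |

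In absolute terms, power of plain Wilcoxon vs van Elteren is 62-75% vs 62-74% with no effect and 55-67% vs 61-70% with a moderate one.

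**Type I error.** Plain Wilcoxon 0.9-6.0%, two-branch rule 1.3-6.2%, van Elteren 3.9-6.3%, ANCOVA 3.9-6.5%. The low values for Wilcoxon show conservatism under a prognostic stratum.

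**A different platelet model** (log scale, 1,000 runs per scenario) points the same way. Plain vs stratified power is 72-76% vs 72-75% with no stratum effect, 68-71% vs 71-73% with a moderate one (0.4 log) and 49-64% vs 65-69% with a strong one (0.8 log). With nadir in the model and scheduled counts only, Shapiro-Wilk rejects in 91-100% of trials when about half or more of subjects have zero days, but in 24-68% when most have some severe days. With near-daily counts it ranges from 4% to 100%.

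**The case against.** A reader might infer three stronger points that the documents do not support.

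- **Step 1 will usually be decided by the Wilcoxon test.** This is a forecast. No distribution is given, the 0.05 switch is assumed, the SAP also relies on a plot, and unscheduled counts may enter the duration. The rejection rates above fall well below one half in some settings.
- **The SAP prescribes an unstratified Wilcoxon test.** It does not mention Wilcoxon. The fallback is found only in the protocol, under another heading, so the two-branch rule is a reading across documents. What the SAP itself lacks is any stated consequence of the normality check.
- **Type I error is at risk.** It is not inflated; the plain test errs on the conservative side.

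The strongest case against acting is that the gain is a conditional matter of efficiency. Nothing in the documents shows that the number of agents predicts duration. The fair comparator is the two-branch rule, against which the gain is small unless the stratum effect is strong. A strong effect is an upper bound, since Protocol 4.1 criterion 4 requires every subject to have had two counts below 50 × 10⁹/L in Cycle X. The main simulation also omits the SAP's rule that a missing scheduled count is treated as low. Adding that rule with 10% premature termination lowers power by about 3-10 points for plain and stratified Wilcoxon alike, usually more than the stratification gain in the none and small cases.

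All of this stands and limits the size of the point. It does not remove it: the missing-count rule leaves the van Elteren advantage in place under moderate or strong effects, and stratifying costs under 1 point of power when the stratum is not prognostic. Van Elteren is not uniformly best: it ranged from 9 points below to 3 points above ANCOVA with stratum and nadir. Its case rests on needing neither normality nor a baseline duration.

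**Conclusion.** The point holds as a cheap improvement of low to moderate priority. The SAP applies a normality check to the Step 1 outcome without saying what follows, and the only fallback documented states no stratification, although randomization, the primary test and the protocol ANCOVA use the stratum. The fallback is likely to apply if many durations are zero, but this is not assured.

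The power at stake is negligible if the stratum is not prognostic and a few points if it is moderately so; only a strong effect makes it large. These sizes rest on assumed platelet distributions, stratum shares and stratum effects, so they serve to compare tests and do not predict Step 1 power. They are also not conditioned on success of the primary test, which must come first.

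**What to change.** Before unblinding, state in SAP 8.2.1 that the rank-based test for Step 1 is the van Elteren test (Wilcoxon stratified by the IWRS number of agents, 1 or ≥2), two-sided at 0.05 on the FAS. Preferably make it the single, unconditional Step 1 test and remove the normality check from the hierarchy, so that neither a pre-test nor a plot reading selects the deciding p-value.

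Report as supportive the mean days per arm and an ANCOVA with treatment, stratum and Cycle X nadir. A baseline measurement has no evident meaning for a duration, and SAP 4.3.4 already supplies a usable covariate: "baseline will be defined as the lowest platelet count collected during the qualifying period in Cycle X".

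The cost is SAP wording and a recorded change from Protocol 10.2.1.3, with no extra data or patients. The downsides are that the deciding result is rank-based, that a Hodges-Lehmann shift may be 0 when many durations are zero (hence the mean days alongside), and that nothing is gained if the stratum is not prognostic.
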